Proposal: Temporal variation in exhaled volatile organic compounds in response to therapeutic intervention in esophageal cancer patients

Principal investigator:

[name] FACS FRCS (c) FRCSE (Hon) FRCSE (Hon)
Head Of Thoracic Surgery and Thoracic Oncology
Director Digestive Disease Institute Esophageal Center of Excellence
President Ryan Hill Research Foundation
Virginia Mason Medical Center
[name]
[name]
[contact]
Email: [contact]

Co-investigator:

[name] [name]
Professor of Surgical Sciences
Head of Division of Surgery
Department of Surgery and Cancer,
Imperial College London,
St Mary's Hospital,
[name]
[contact]
E-mail: [contact]

**APPROVED
06/29/2020
BRI IRB**

SPECIFIC AIMS

Hypothesis: we hypothesize that cancer-associated Volatile Organic Compounds (VOCs) will vary significantly following therapeutic intervention in patients with esophageal cancer (EC) and that variation will predict treatment response.

Primary aim: to determine longitudinal variation in exhaled VOC concentrations during intended curative therapy for EC cancer.

Secondary aims:

- i. To validate the previously published model for a exhaled VOC breath test of EC cancer
- ii. To correlate the exhaled VOCs of EC cancer patients to important clinical parameters
- iii. To determine the relationship between exhaled VOCs and response to neoadjuvant chemoradiotherapy
- iv. To study changes in exhaled VOCs following tumor resection and their association with disease recurrence.
- v. To correlate the exhaled and urinary VOC concentrations in EC cancer patients
- vi. To longitudinal variation in the upper gastrointestinal microbiome and its relationship to exhaled and urinary VOC concentrations.

STUDY OUTCOMES

Primary outcome

- i. Confirmation of exhaled and urinary VOC biomarkers of EC cancer

Secondary outcomes

- i. Verification of changes in VOC concentrations that occur in response to therapeutic intervention
- ii. Refine diagnostic model for the detection and monitoring of EC cancer through analysis of exhaled VOCs
- iii. Linkage of longitudinal VOC data to predominant upper gastrointestinal bacterial species
- iv. Patient acceptability of breath test

BACKGROUND AND SIGNIFICANCE

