Background: The global prevalence of esophageal cancer (EC) in 2016 was 2.75 million cases with an estimated 1.60 million new cases and 1.25 million deaths during the same year (1, 2). Early EC cancer typically has non-specific symptoms that are commonly ascribed to benign conditions. Current guidelines recommend referral for endoscopy, only in the setting of 'red flag' symptoms that are frequently associated with inoperable disease. As a consequence, 7 out of 10 new cases of EC cancer diagnosed are considered to be at an advanced stage with less than 1 in 3 patients eligible for potentially curative therapy and less than 1 in 5 patients alive at 5 years (3).

Volatile organic compounds and EC cancer biomarkers:

Our approach to this clinical challenge is to establish a non-invasive test for the detection of EC cancer that is based upon the unique signature of volatile organic compounds (VOCs) within exhaled breath.

Volatile organic compounds (VOCs) are carbon-containing molecules that are sufficiently volatile to be detectable in a gas form at room temperature. VOCs may emanate from numerous sources within the human body as well as our local environment. Established uses of VOC measurements include the assessment of environmental contamination, the flavor and fragrance industries and in counter-terrorism. There is now established evidence that VOCs which are released from the human body in breath and urine can be used as a non-invasive method of detection and monitoring (patho)physiological processes.

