The proposed study will be conducted in collaboration with the volatile biomarker research group, based at St Mary's Hospital (Imperial College London). The primary focus of this group's research has been the non-invasive diagnosis of gastrointestinal cancer through the detection of VOCs within exhaled breath. They have previously established diagnostic models of gastroesophageal and colorectal cancers (8, 9, 15, 16). In a recent multicenter validation study they demonstrated a diagnostic performance of a breath test for gastroesophageal cancers based on five VOCs, with an area under the receiver operator characteristic curve of 0.85 and sensitivity and specificity of 80% and 81% respectively (15). Their previous work has alluded to importance of volatile fatty acids, aldehydes and phenols as tumor markers. In parallel to these clinical trials they have sought to investigate the mechanisms whereby VOCs are deregulated in cancer by undertaking carefully designed in-vitro and in-vivo studies. Specifically they have demonstrated an association between gastroesophageal cancer, its predominant associated bacterial species (E.coli, K. pneumoniae and S. anginosus) and VOCs production (unpublished data). Whilst these findings give support to the hypothesis that cancer has associated bacteria, no study has sought to directly compare the intestinal microbiome and exhaled VOC levels.

Critical knowledge gap: Previous studies have established an important link between deregulated VOC production and EC. These studies have all assessed exhaled VOCs at a single point in time using a cross-section study design. Longitudinal variation in exhaled and urinary VOCs, the contribution of the upper gastrointestinal microbiome and the effect of therapeutic intervention in EC cancer patients remain unknown. An understanding of this variation is critically important in establishing intra-subject variability and likely mechanisms of VOC production and release. Furthermore the expected decline in target VOCs following chemoradiotherapy and/or tumor resection would both verify the link between the tumor and aberrant VOCs production as well as offering an opportunity to utilize VOCs as a means to assess treatment response including the early detection of recurrence.

RESEARCH DESIGN AND METHODS

Study design: longitudinal cohort study

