Sample size: 50 curative tri-modality patients. Study sample size has been determined pragmatically based on estimated patient recruitment during the course of 1 year in a high volume center for the management of EC

Human subjects: patients undergoing potentially curative therapy for EC cancer at Virginia Mason Medical Center who meet the eligibility criteria will be invited to participate in this study.

Inclusion criteria: patients with the following characteristics will be eligible for inclusion in this study:

- i. aged 18-90 years
- ii. newly diagnosed, treatment naïve patients with esophageal and/or gastroesophageal junctional cancer
- iii. planning to undergo curative treatment, including neoadjuvant chemoradiotherapy and surgical resection

Exclusion criteria: patients with the following characteristics will not be eligible for inclusion in this study:

- i. pregnant females
- ii. without malignant esophageal disease
- iii. malignancy at a secondary site other than the esophagus
- iv. patients undergoing palliative treatment for esophageal cancer
- v. patients not receiving neoadjuvant chemoradiotherapy and surgical resection for esophageal cancer
- vi. inability or unwillingness to provide written informed consent

Study time points: subjects will be asked to provide exhaled breath, urine and saliva samples at the following time points during their routine care:

- i. Before commencing treatment for esophageal cancer*
- ii. Following conclusion of neoadjuvant therapy (at the time of a routine outpatient appointment or on the day of surgery)
- iii. Following surgical resection (after the removal of the nasogastric tube, during the inpatient hospital stay)
- iv. At the time of routine postoperative follow-up at VM (between six months to one-year following surgery)

Subjects will also be asked to complete an engagement questionnaire at one of the study timepoints. See "Subject Engagement" section of the protocol.

*Where feasible at the time of initial breath sampling subjects will be asked to provide breath samples on two separate routine clinical appointments (often on consecutive days) in order to assess short-term temporal variation in exhaled VOC levels. At the

time of their initial assessment it is common for patients to have routine clinical appointments on consecutive days.

Any data that are not able to be collected with reasonable efforts will not be considered protocol deviations.

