Exhaled breath collection and analysis: Subjects will be asked to fast for a minimum of 1-2 hours prior to breath sampling, with an ideal fast of 4 hours or longer. Where possible sampling will be performed on a day when subjects are fasting as part of their routine care (e.g. prior to CT-PET or endoscopy). Before breath sampling, subjects will also be asked to rinse their mouth with water. Following a period of relaxed tidal breathing subjects will be asked to exhale directly in to double thickness Nalophan® bags (Scentroid, Canada).

Breath samples will be immediately (within 30-120 mins of collection, target: 30 minutes) transferred from Nalophan sample bags to thermal desorption (TD) tubes (Markes International, Llantrisant, UK) pre-packed with 200 mg of Tenax and 100 mg of Carbograph 5. 500ml aliquots of breath will be transferred to four TD tubes via a handheld precision pump (Easy-VOC, Markes International, Llantrisant, UK). TD tubes will be securely capped and stored at -80°C prior to being transferred to Imperial College London for analysis.

TD tubes containing exhaled VOCs will be analyzed by Gas Chromatography Mass Spectrometry (GC-MS). For thermal desorption GC-MS analysis, adsorbent tubes will be loaded into a sample tray (TD-100, Markes International). The tube will be dry-purged for 1 minute to remove excess moisture and air. VOCs will be desorbed from the tube by a specific combination of heat and gas flow and will be refocused on the cold-trap. The cold-trap is then rapidly heated to 290°C with carrier gas flow so that VOCs are transferred to the GC column in a narrow band. For separation, the GC column will be ramped. The mass spectrometer will run in electron impact ionisation mode, scanning mass ions 20-250 m/z. An initial solvent delay will minimize interference from water. Chromatographic data will be analyzed using the Mass Hunter package (Agilent Technologies) in combination with the NIST mass spectral library (2014, Maryland, USA) for compound identification and semi-quantification.

Urine sampling and analysis: Patients will be asked to provide a clean catch urine sample (approximately 10ml) into a sterile sample container. Urine samples will be aliquoted and stored at -80°C prior to being transferred on dry ice to Imperial College London for analysis.

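### No thermal desorption tube is assigned to room air and sampling location is not recorded, so a change in ambient VOCs cannot be separated from a treatment change at the inpatient post-resection time point

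*Protocol*

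**What the plan says.** The primary aim is "to determine longitudinal variation in exhaled VOC concentrations during intended curative therapy for EC cancer" (Protocol, Specific Aims). The paragraph on the critical knowledge gap goes further and says that "the expected decline in target VOCs following chemoradiotherapy and/or tumor resection would both verify the link between the tumor and aberrant VOCs production".

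The background on volatile organic compounds says that "VOCs may emanate from numerous sources within the human body as well as our local environment".

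Under Study time points, the settings are:
- **Baseline (i):** where feasible, "subjects will be asked to provide breath samples on two separate routine clinical appointments (often on consecutive days").
- **After neoadjuvant therapy (ii):** "at the time of a routine outpatient appointment or on the day of surgery".
- **After resection (iii):** "after the removal of the nasogastric tube, during the inpatient hospital stay".
- **Late follow-up (iv):** a routine visit at the same center, six months to one year after surgery.

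Exhaled breath collection and analysis specifies the fast, mouth rinse, bag, transfer time, sorbent masses, pump and storage temperature. On the tubes it says that "500ml aliquots of breath will be transferred to four TD tubes". It mentions no room-air sample, bag or tube blank, filtered inspired air or fixed sampling room. Patient demographics and metadata lists the fasting duration but not the sampling location. Statistical analysis names no background correction.

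**The concern.** A within-patient comparison removes whatever stays constant in a patient. It does not remove something that changes with the visit in the same way for everyone. At time point iii all patients are on the inpatient stay, so any systematic difference between the air there and the air at outpatient appointments coincides with the effect of resection. A larger sample would not help, because this would be bias and not random error.

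The inference at stake is the one the protocol values most: that a fall in target VOCs after treatment shows they come from the tumor. If a change in inhaled air can give the same signal, that reading is not secure at time point iii. Secondary aim iv (change after resection) draws on the same samples. The gap cannot be closed at analysis, since air that was never sampled cannot be adjusted for.

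**Working it through.** **Step 1. Is setting tied to treatment stage?** Taking the contrasts one at a time:
- *i or ii against iii, and iii against iv:* time point iii is inpatient for every patient, and i and iv are routine appointments. Against those two, setting and stage coincide completely. Against ii the setting also changes, at least for patients sampled as outpatients.
- *i against ii:* time point ii mixes outpatient visits and the day of surgery, in proportions that are not stated. Setting is tied to stage only in part.
- *i against iv:* both are routine appointments at the same center. No difference in setting is shown.

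**Step 2. Could the data separate the two sources?** All four tubes hold breath, so the inhaled background is not measured under this protocol. Location is not a listed field, so adjustment for it is not provided for either. The repeat baseline samples estimate short-term variation before treatment; they say nothing about the air on the ward.

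**Step 3. How much could it matter?** The protocol states no figure to reproduce: the 50 patients are a pragmatic number, with no alpha, SD or effect size. The following is an illustration. Inputs: n = 50 complete pairs (from the protocol's sample size); a two-sided 5% paired t-test, a true treatment effect of zero, and a setting shift of d SDs of the paired difference (all assumed).

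With λ = d√n and t* = t(0.975; n − 1), the rejection probability is

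P = 1 − F(t*; n − 1, λ) + F(−t*; n − 1, λ),

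where F is the noncentral t distribution function. For d = 0.2 and n = 50, λ = 0.2 × √50 = 1.41 and P = 28.4%.

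| Assumed shift d | 50 pairs | 30 pairs |
|---|---|---|
| 0 | 5% | 5% |
| 0.1 | 10.7% | 8.3% |
| 0.2 | 28.4% | 18.5% |
| 0.3 | 54.8% | 35.5% |
| 0.4 | 79.2% | 56.3% |
| 0.5 | 93.4% | 75.4% |

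For time point ii, if a fraction f of patients is sampled on the day of surgery, the mean shift is f × d. With d = 0.5 and 50 pairs, P is 13.9% at f = 0.25 (mean shift 0.125), 41.0% at f = 0.5 (mean shift 0.25) and 93.4% at f = 1. This counts the mean shift only and ignores the extra spread that a mixture creates, so the values for f below 1 are slightly high.

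**Step 4. What would giving up one breath tube cost?** Assume the tubes are replicates that are averaged, with visit variance 1 and tube variance v. The variance of a visit mean with k tubes is 1 + v/k.
- v = 0.11: 1 + 0.11/4 = 1.0275 and 1 + 0.11/3 = 1.0367; ratio 1.009, a rise of 0.9%.
- v = 0.56: 1 + 0.56/4 = 1.14 and 1 + 0.56/3 = 1.1867; ratio 1.041, a rise of 4.1%.

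These tube variances are assumptions. They equal 0.11/1.11 = 10% and 0.56/1.56 = 36% of visit plus tube variance.

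**The case against.** Four points can fairly be made on the other side.

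- *Room air may be handled elsewhere.* The background refers to existing standardized, quality-controlled protocols for breath sampling, which are not at hand. Blanks or room-air samples might be described there. That sentence does not mention ambient air, however, and this protocol's own collection section assigns every tube to breath. The supportable statement is that this protocol assigns none to room air, not that none will ever be taken.
- *The settings are partly inferred.* This stands. The advice to sample before CT-PET or endoscopy where possible fixes a fasting day, not a room, and is not confined to baseline. Only time point iii has a distinct setting for everyone.
- *No ambient difference is demonstrated.* This stands too. The protocol gives no room-air levels for its target compounds (fatty acids, aldehydes, phenols). The percentages above are simply the power of a t-test against an assumed shift, for one VOC and with complete pairs, whereas the protocol expects some data to go uncollected.
- *The statistical analysis plan may deal with it.* An adjustment could be specified there, but only for background air that was collected. Collection is fixed in the protocol.

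A reader might infer that location differences do bias the longitudinal comparison at all four time points, and so the whole primary aim. The documents do not support that: they show that the two sources cannot be separated at iii, and partly at ii, and they do not show that the air differs.

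**Conclusion.** The point holds in a limited form. Followed as written, the protocol cannot separate a change in room air from a treatment-related change in contrasts involving time point iii, and in part those involving time point ii. Baseline against time point iv is not shown to be affected. The point concerns exhaled VOCs; urine is measured in the headspace of sealed vials in the laboratory.

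Size and direction are unknown. Under the stated assumptions, a shift as small as 0.1 SD about doubles the nominal 5% error for one VOC, and 0.4 SD raises it to about 79% with 50 complete pairs. These figures show sensitivity and do not estimate the actual bias. The remedy costs little and must be in place before samples are taken, so the change is worth making.

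**What to change.** In Exhaled breath collection and analysis, assign one of the four planned tubes per visit to a 500 ml room-air sample, taken where and when the breath is collected and ideally passed through the same type of bag so that it is comparable with the breath tubes. In Patient demographics and metadata, add the sampling location for each sample. VOCs explained by ambient air can then be flagged in the longitudinal analysis; the exact rule or adjustment can be left to the analysis plan. If a separate procedure already collects room air, a sentence citing it would serve.

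**Cost:** no additional tube or laboratory run and nothing more asked of the patient, but one breath tube fewer per visit (the 1% to 4% loss above, if the tubes are replicates) and one more data field. The protocol does not say where the transfer from bag to tube takes place, so the pump may have to be taken to the ward.

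The protocol also does not say what each of the four tubes is for. If the fourth is reserved for another purpose, the alternative is one fixed sampling room where feasible, with the location recorded for every sample.

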VOCs within the headspace gas above urine samples sealed in air-tight vials will be analyzed by GC-MS. Urine samples (2ml) will be diluted in 6ml deionized pure water, acidified using HCl to pH 2.0. Urine osmolality (OsmoPRO®, Advanced Instruments, Norwoor, UK) will be analyzed for the purpose of subsequent standardization. Samples will be placed in air tight headspace vials into which a HiSorb probe (Markes International, Llantrisant, UK) will be inserted. Headspace vials including the HiSorb probe will be heated and agitated at 60°C for 30 minutes. Headspace VOCs extracted

onto HiSorb probes will be analyzed using an Agilent 7890B GC with 5977 MSD (Agilent Technologies, Cheshire, UK) coupled to a Markes TD-100 device.

Saliva sampling and analysis: Subjects will be asked to fast for a minimum of 1-2 hours (Target: 4 hours) prior to saliva sampling. Where possible saliva sampling will be performed on a day when subjects are fasting as part of their routine care (e.g. prior to CT-PET or endoscopy). Saliva samples (1-3ml) will be collected by asking subjects to spit into a sample pot. Saliva samples will be aliquoted and stored at -80°C prior to being transferred on dry ice to Imperial College London for analysis.

Bacterial RNA will be extracted from saliva samples and analyzed by 16S rRNA gene amplicon sequencing to identify the species composition. Bacterial community types derived from tissues biopsies will be identified by cluster analysis of compositional data from 16S rRNA sequencing. Bacterial interaction networks will be constructed to identify any keystone species.

Patient demographics and metadata: essential accompanying patient demographics and metadata will include: age; sex; comorbidities; height; weight; tumor histology and stage; details of (neo)adjuvant therapy; details of surgery; duration of pre-test fasting, and; radiological parameters (tumor dimensions, nodal burden and PET-standardized uptake value). Where possible, data will be obtained via the IRB approved institutional database (IRB18-076).

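### Smoking is neither recorded nor restricted at any sampling visit, so for a VOC that smoking raises, abstinence by the inpatient sample could be mistaken for part of a tumor effect

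*Protocol*

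**What the plan says.** The primary aim (Protocol, Specific Aims) is "to determine longitudinal variation in exhaled VOC concentrations during intended curative therapy for EC cancer". The design is given as "Study design: longitudinal cohort study", with breath, urine and saliva taken at four time points. The first is before any treatment, at routine appointments. The third is defined as "Following surgical resection (after the removal of the nasogastric tube, during the inpatient hospital stay".

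The Background accepts that "VOCs may emanate from numerous sources within the human body as well as our local environment". It also reports that earlier work pointed to "volatile fatty acids, aldehydes and phenols as tumor markers". Under Critical knowledge gap, the expected decline in target VOCs after chemoradiotherapy or resection "would both verify the link between the tumor and aberrant VOCs production".

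On control of other influences:

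- **Eligibility:** three inclusion and six exclusion criteria; none concerns smoking.
- **Exhaled breath collection and analysis:** a fast, a water mouth rinse and relaxed tidal breathing; no instruction on smoking.
- **Patient demographics and metadata:** "age; sex; comorbidities; height; weight; tumor histology and stage; details of (neo)adjuvant therapy; details of surgery; duration of pre-test fasting", then radiological parameters; no smoking item.
- **Subject engagement:** one survey, on understanding and opinions of breath testing.

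The Human Subject section states that, apart from the survey, all other data come from routine care and the medical record. Data are to be drawn from the institutional database IRB18-076 where possible, but its fields are not described.

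**The concern.** Comparing each patient with himself or herself removes fixed differences between patients. It does not remove an exposure that changes along with the stage of treatment. Smoking could be such an exposure: a patient who smokes at the outpatient baseline may have stopped before surgery and is unlikely to smoke on the ward. If smoking raises a given VOC, that patient's level falls between the first and third time points whether or not the tumor contributes.

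Such a fall has the same sign as the expected tumor effect and appears at the same visit. The study has one cohort and no parallel untreated group, and the protocol is ready to read a decline as evidence of tumor origin. At stake is therefore the interpretation of the primary aim, for whichever VOCs are affected. An analysis plan cannot repair this later, because exposure on the day of sampling has to be asked about on that day.

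**Working it through.** **Is there a figure to reproduce?** No. The protocol says "Study sample size has been determined pragmatically based on estimated patient recruitment during the course of 1 year" and gives no effect size, standard deviation, smoking rate or smoking effect. The numbers below are illustrations on assumed values.

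**Does another part of the protocol fill the gap?**

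- The paired baseline samples are both taken before treatment, often on consecutive days. They measure short-term variation, not a later change in smoking.
- Subjects who turn out not to have tri-modality treatment are sampled when possible and are for comparison only. They do not reproduce abstinence around surgery.
- Fasting duration is recorded, so the protocol already accepts that a pre-sampling exposure should be documented. Smoking does not get the same treatment.

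**Size of a spurious fall.** Let s be the share smoking at baseline, a the fraction of smokers abstinent by time point iii, and r the ratio of the VOC when smoking to when not. With no tumor effect, the mean log change is −s × a × ln r, and the fall in the geometric mean is 1 − exp(−s × a × ln r).

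| s | r | a | s × a × ln r | Fall |
|---|---|---|---|---|
| 0.15 | 1.5 | 0.5 | 0.030 | 3% |
| 0.15 | 1.5 | 1 | 0.061 | 6% |
| 0.25 | 2 | 0.5 | 0.087 | 8% |
| 0.25 | 2 | 1 | 0.173 | 16% |
| 0.35 | 3 | 0.5 | 0.192 | 17% |
| 0.35 | 3 | 1 | 0.385 | 32% |
| any | 1 | any | 0 | 0% |

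**Could a shift of this kind produce a significant result at n = 50?** A paired t-test was simulated (two-sided 0.05, 20,000 runs, no tumor effect, SD of the paired log difference set to 1). A share of patients stop smoking, and each of them falls by e SD. The chance of a significant fall, against 2.5% nominal in that direction, is:

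| Share stopping | e = 0.5 | e = 1.0 | e = 1.5 |
|---|---|---|---|
| 10% | 5% | 10% | 15% |
| 20% | 10% | 25% | 43% |
| 30% | 17% | 47% | 73% |

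These are rates per affected VOC. The two tables cannot be joined, because the documents give no within-patient SD with which to turn a ratio into SD units.

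**The case against.** A reader might infer that smoking will go unrecorded and that its effect could never be separated from the tumor's. The documents do not support that. The metadata sentence says what will be included; it does not exclude other items. The database, the medical record or the comorbidities field may hold a smoking history. The standardized breath-sampling protocols mentioned in the Background are not shown either. With a baseline history, analysts could restrict to never-smokers. What stands is narrower: this protocol does not require smoking to be recorded, and a chart history would not reliably give exposure on each sampling day.

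A reader might also infer that a fall seen in this study will be due to smoking. No passage says that smoking raises the target compounds or that patients stop around surgery; both are general reasoning. The Background names volatile fatty acids (butanoic, pentanoic and hexanoic acid) as raised in these patients, and a VOC that smoking leaves alone is not biased. The argument on timing is also strongest for the inpatient sample. Nothing in the documents shows systematic abstinence after neoadjuvant therapy or at six to twelve months. These limits hold, and they restrict the point to what could happen.

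It is also fair that the sentence on verifying the tumor link is background rationale and not an analysis rule, that sensitivity analyses usually belong in the SAP, and that drugs, diet and hospital air are also not listed. None of this removes the need to collect the exposure prospectively, and that is a matter for the protocol.

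**Conclusion.** The point holds as a gap in data collection that should be closed. The protocol leaves an exposure that can vary with treatment stage unrestricted, and does not require it to be recorded, in a single-cohort before/after study whose primary aim is within-patient change. For VOCs that smoking raises, abstinence between baseline and the inpatient sample could be mistaken for part of a tumor effect.

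The size is unknown from the documents. The range of about 3% to 32% rests wholly on assumed smoking prevalence (15% to 35%), ratio (1.5 to 3) and abstinence (half to all), and the bias is zero for unaffected VOCs. Confidence is medium: the omission is certain from the text, but its consequence depends on facts outside it.

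**What to change.** 1. Add to the essential metadata, at every time point: current smoking or vaping (yes/no) and hours since last use.
2. Add to the breath-sampling instructions a request not to smoke or vape during the pre-sampling fast, and record departures.
3. Repeat the longitudinal comparison in subjects who did not smoke at either time point compared, or adjust for smoking status at each visit. Report estimates with confidence intervals beside the main result.

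Do not adopt a rule that denies a tumor origin to any change seen only in subjects whose smoking changed. At an assumed 25% prevalence that group has about 0.25 × 50 = 12.5 subjects at most. A change that is apparent in one small subset and not in another is not a sound criterion.

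**Cost:** two questions per visit and one extra analysis. The restricted analysis is less precise. With complete follow-up, equal SD and 15%, 25% or 35% of subjects excluded, its confidence interval widens by a factor of about √(1/0.85) = 1.08, √(1/0.75) = 1.15 or √(1/0.65) = 1.24.
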